3.1 Study Design

Type of design: Prospective open label study

Provide brief overview of the study phases:

- **Visit 1 Baseline MCC:** Participants will inhale Tc99m-SC, assessment of MCC over a 2-hour period to define baseline MCC. Participants will then perform spirometry, followed by sputum induction.
- **Visit 2 Follow-up Baseline Visit:** Participants will return the following morning for a query of symptoms overnight. Spirometry will be performed. Participants will sit in front of the gamma camera for 30 minutes to estimate retention of Tc99m-SC in the airways.
- **Visit 3 Albuterol Treatment visit:** Between 1-6 weeks of the baseline visit, participants will return to the lab to complete spirometry and the symptom questionnaire. They will then inhale Tc99m-SC and immediately be scanned by gamma scintigraphy to measure deposition of the radiolabeled particles in the airways (4 minute scan). While they remain seated in front of the gamma camera they will then inhale 4 puffs of albuterol. MCC measurement will be performed for a 2-hour period post-radioaerosol inhalation to measure acute effects of albuterol on MCC. Subjects will undergo sputum induction at the completion of the MCC scan.
- **Visit 4 Follow-up Albuterol Treatment Visit:** Participants will return the following morning for a query of symptoms overnight. Spirometry will be performed. Participants will sit in front of the gamma camera for 30 minutes to estimate retention of Tc99m-SC in the airways.
- **Visit 5: 7% HS concentration comparison:** Participants will return to the lab
- Between 1-6 weeks of the albuterol visit, participants will return to the lab to complete spirometry and the symptom questionnaire. They will then inhale Tc99m-SC and immediately be scanned by gamma scintigraphy to measure deposition of the radiolabeled particles in the airways (4 minute scan). While they remain seated in front of the gamma camera they will then inhale 4 puffs of albuterol followed by 4 mL of nebulized 7% HS. MCC measurement will be performed for a 2-hour period post-radioaerosol inhalation (which includes the period of HS inhalation) to measure acute effects of HS on MCC. Subjects will undergo sputum induction at the completion of the MCC scan.

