temperature, respiratory rate (RR), heart rate (HR), oxygen saturation, blood pressure (BP), and symptom questionnaires will be collected. Fractional exhaled Nitric Oxide (FeNO) will be measured in exhaled breath (used to classify asthma as being predominated by eosinophilic vs non-eosinophilic airway inflammation). Spirometry will be performed to establish that day's baseline values. FEV1 must be $\geq 70\%$ before albuterol. Participants will inhale Tc99m-SC and immediately be scanned by gamma scintigraphy to measure deposition of the radiolabeled particles in the airways (4 minute scan). MCC will be assessed over a 2-hour period to define baseline MCC. A baseline symptom questionnaire will be obtained. Subjects will then undergo a sputum induction procedure

Any subject who experiences a $\geq 10\%$ reduction in FEV1 from that day's baseline at the spirometry measure, or who increases HR, BP or RR more than 30% from baseline, or with audible wheezing on physical exam, or participants who report any symptom as severe (score of 3) on the symptom questionnaire will be considered intolerant to HS and will not be included in further study. Oxygen saturation will be monitored, and a transient decrease is an expected finding when using mucolytic agents. Sustained ($< 90\%$ for more than 1 hour) decrease in oxygen saturation will be considered intolerance. Testing will be stopped at any point the volunteer requests that it stop. Any subject who does not tolerate HS will be monitored until the vital signs return to normal limits, and the symptoms resolve. Subjects will be discharged to home with contact information for a study physician, an asthma action plan reviewed by the study coordinator, and emergency medications if needed overnight, including an albuterol MDI with spacer and 60 mg of prednisone. Subjects will be instructed to call the physician on call if they require prednisone treatment.

4.2 Visit 2 Follow-up Baseline Visit: Participants will return the following morning for vital signs, symptom questionnaire, 24-hour lung retention imaging, FeNO, and spirometry. Subjects who tolerate the HS dose and do not meet stopping criteria will be invited back for the remaining study visits.

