airways (i.e. not from the back of the throat) is ready for expectoration. Prior to expectoration, subjects will be asked to blow their nose, rinse their mouth with water, and clear their throat to avoid the inclusion of non airway fluid samples. The sample will be expectorated into a sterile specimen jar and capped.

Following the measurement of FEV1 after the first 7 minute inhalation period, the concentration of saline will be increased from 3% to 4%, provided the FEV1 decrement is < 10% from the post bronchodilator value. If the FEV1 falls between 10-20% of the post bronchodilator value, the test will proceed but the concentration of saline will remain the same. If the FEV1 falls by > 20% or if troublesome symptoms occur, the nebulization will be discontinued, and albuterol will be immediately available if necessary to relieve symptoms. The same procedure will be followed for the final 7 minute inhalation period using 5% hypertonic saline provided the FEV1 safety parameters described above have been met. The nebulization is stopped after a total of 21 minutes or earlier if a sputum sample of good quality is obtained (i.e. visible sputum plugs). Subjects may request early termination at any time the procedure becomes intolerable.

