Protections to Minimize Risk of Spirometry:

Subjects will be seated in a non-rolling chair when spirometry is performed and standard methodology conforming to the American Thoracic Society guidelines for measurement of spirometry will be used. Subjects will be instructed to notify the study staff if they feel lightheaded, and albuterol will be available in the event the subject experiences any unanticipated bronchoconstriction.

Protections to Minimize Risk of Mucociliary clearance scan:

Radiation history is collected. Any subject who will exceed safe annual exposure limits will not be enrolled.

Protections to minimize Risk of Sputum Induction:

Subjects will have been given 4 puffs of albuterol in the 2-3 hour time period prior to sputum induction. In the event of bronchospasm associated with the induction, albuterol will be

immediately available for rescue.

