14. APPENDIX

Study Personnel:

Role in Project	Name and Address	Title
Principal Investigator	[name], MS CEMALB, [name]	Professor of Pediatrics & Director, Center for Environmental Medicine, Asthma and Lung Biology
Co-investigator	[name] [name]	James C. Moeser Eminent Professor of Medicine & Director of the Marsico Lung Institute
Co-investigator	[name] CEMALB, [name]	Professor of Medicine, Director of Mucociliary Clearance and Aerosol Research Lab, CEMALB

Summary of Study Procedures:

Study Procedures	Visit 1: Baseline MCC Visit	Visit 2: (24h f/u)	Visit 3: Albuterol and MCC	Visit 4: (24h f/u)	Visit 5: Acute 7% HS	Visit 6 (24h f/u)	Study Completion visit
Time between visits	1-6 weeks		1-6 weeks		5-10 days		
Informed Consent	X						
History, med review	X		X		X		X
Review history, AEs	X	X	X	X	X	X	X
Vital Signs	X	X	X	X	X	X	X
Symptom Questionnaire	X	X	X	X	X	X	X
Physical exam	X		X		X		
Urine pregnancy test	X		X		X		
Spirometry	X	X	X	X	X	X	X
Albuterol	X		X		X		
Nebulized HS					X		
MCC Measurement	X		X		X		
24h Lung Retention Images		X		X		X	
Induced Sputum Collection	X		X		X

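### The protocol contradicts itself on whether, and when, albuterol is given at Visit 1, which affects the cover and FEV1 reference for that visit's sputum induction and could change the reference scan

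*Combined protocol and SAP*

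**What the plan says.** Some places describe Visit 1 without albuterol:

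- Section 3.1, Visit 1: "Participants will inhale Tc99m-SC, assessment of MCC over a 2-hour period to define baseline MCC". The next step is: "Participants will then perform spirometry, followed by sputum induction".
- Section 4.1 gives the same order in more detail: "MCC will be assessed over a 2-hour period to define baseline MCC", then a questionnaire, then induction. No dosing step appears.
- The synopsis (Study Design and Study Phases) introduces albuterol as what the second scan adds. The baseline image-capture description in Section 5 has no dose either.

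Other places presume albuterol at Visit 1, or at every induction:

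- The procedures table in the Appendix has an albuterol row marked at Visits 1, 3 and 5. The first mark is in the column "Visit 1: Baseline MCC Visit". The nebulized HS row is marked at Visit 5 only.
- Section 4.1 places the Visit 1 FEV1 threshold "before albuterol. Participants will inhale Tc99m-SC and immediately be scanned by gamma scintigraphy".
- Section 9, on protections for sputum induction: "Subjects will have been given 4 puffs of albuterol in the 2-3 hour time period prior to sputum induction". No visit is excepted, and the synopsis and table put an induction after every MCC scan, Visit 1 included.
- Section 5, induction procedure: the saline concentration is raised "provided the FEV1 decrement is < 10% from the post bronchodilator value". The hold and stop rules that follow are part of the same stepwise FEV1 check.

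Section 6.1 defines the primary endpoint, and 6.2 the albuterol endpoint, as changes from baseline MCC, which is measured at Visit 1.

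**The concern.** Two things depend on the answer.

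The first is the conduct of the Visit 1 induction. Subjects with moderate to severe asthma inhale 3% to 5% saline under a stated protection and an FEV1 rule that both presuppose a bronchodilator. Staff who work from the narrative would give none before that induction. Staff who work from the table might give one. The two groups would act differently and would measure FEV1 falls from different starting values.

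The second is the meaning of the baseline scan. It is the reference for the primary contrast and for the albuterol contrast. Whether albuterol was active during it decides what those contrasts estimate. If practice varied between subjects, the reference would be a mixture of the two conditions.

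**Working it through.** No figure in the plan can be reproduced on this point, because the sample-size calculation in 6.4 does not depend on it. The check is one of sequence and of what each contrast estimates.

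**Step 1: timing at Visit 1.** Take the start of the 2-hour scan as minute 0, so it ends at minute 120. Let induction begin at minute 120 + s, where s is the time for spirometry and the questionnaire. The documents do not give s. The Section 9 window can be read in two ways.

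- Between 2 and 3 hours before induction: the dose falls from (120 + s) − 180 = s − 60 to (120 + s) − 120 = s. It is given before the scan or in its first s minutes, so it precedes or accompanies the scan.
- At any point within the preceding 2 to 3 hours: the dose may fall as late as just before induction. That includes the gap from minute 120 to minute 120 + s, after the scan.

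The wording does not settle which is meant.

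**Step 2: the same sentence at Visits 3 and 5.** There albuterol follows the 4-minute deposition image, so induction comes about 120 − 4 + s = 116 + s minutes later, which is roughly 2 hours. The Section 9 sentence fits those visits. Visit 1 is the one where no narrated dose supports it.

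**Step 3: the FEV1 reference.** Section 3.1 goes from scan to spirometry to induction, and Section 5 measures FEV1 before induction. With no dose, that pre-induction value is not post-bronchodilator. The step rule then has no defined reference at Visit 1.

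**Step 4: what the contrasts estimate.** Write U for mean average retention in an untreated scan, A for a scan with albuterol as at Visit 3, AH for albuterol plus HS as at Visit 5, and A* for a Visit 1 scan with albuterol active at whatever dose and time applied.

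| Visit 1 albuterol | Visit 3 − Visit 1 | Visit 5 − Visit 1 | Visit 5 − Visit 3 |
|---|---|---|---|
| None | A − U | AH − U | AH − A |
| Before or during scan | A − A* | AH − A* | AH − A |
| After scan, before induction | A − U | AH − U | AH − A |

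In the first and third rows the primary contrast is HS plus albuterol against no treatment: AH − U = (AH − A) + (A − U). In the second row it is HS added to albuterol. The two versions differ by (AH − U) − (AH − A*) = A* − U, the shift that albuterol produces in the baseline scan. Each retention point of that shift moves the primary contrast by one point, against the 7-point difference targeted in 6.4. The documents give no value for the shift.

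**The case against.** The strongest reply is that the baseline scan is well enough described. The synopsis, 3.1, 4.1 and the image-capture text in Section 5 all describe it without albuterol, and the synopsis treats albuterol as the addition at the second scan. The contrary evidence also has innocent readings. The FEV1 phrase in 4.1 may only restate the pre-bronchodilator eligibility threshold in 3.4. The table mark is untimed and could refer to the inhaler handed out at discharge (4.1, 4.9). The Section 9 sentence fits Visits 3 and 5 and may have been written with those in mind. A dose between scan and induction would satisfy Section 9, the table and the Section 5 rule together and leave both MCC contrasts as narrated.

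Most of this stands as far as the scan is concerned. A reader might infer that the MCC reference has no definition at all, or that Section 9 proves albuterol was on board during the baseline scan. The documents support neither: the scan narratives agree with each other, and the Section 9 window admits a dose after the scan.

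It does not remove the contradiction. None of the innocent readings is written down. If no dose is given at Visit 1, Section 9 and the post-bronchodilator reference are wrong for that induction. If a dose is given after the scan, the narratives omit it.

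It is also true that Visit 5 minus Visit 3 isolates HS and does not use Visit 1. But 6.3 makes that comparison exploratory, while the primary endpoint in 6.1 uses the baseline.

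**Conclusion.** The contradiction is real and should be resolved. For the Visit 1 induction it is direct: the narrated visit provides neither the bronchodilator cover stated in Section 9 nor the FEV1 reference used in Section 5. For the MCC contrasts the effect is conditional. Only a dose before or during the baseline scan changes what Visit 3 minus Visit 1 and Visit 5 minus Visit 1 estimate. The narratives point away from that, but no passage states the timing.

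No numerical size can be attached, because the documents give neither an albuterol effect on retention nor a Visit 1 dose or time.

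Two further inferences should be resisted. One is that the albuterol contrast would be exactly zero if albuterol were active at Visit 1. That needs the same dose and timing effect as at Visit 3, which nothing states. The other is that this inconsistency inflates the false-positive rate for HS. An albuterol contribution to Visit 5 minus Visit 1 arises under the narrated design, where HS is openly given after albuterol, and it would remain if the wording were reconciled to the narrative.

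The conclusion assumes that the albuterol row of the table has been read correctly from the document.

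**What to change.** - Reconcile 3.1, 4.1, the induction procedure in Section 5, the induction protections in Section 9 and the procedures table, so that all five agree on Visit 1. Which procedure applies is for the investigators to decide; this point does not say.
- State whether albuterol is given at Visit 1 and, if so, when relative to the scan. Record the time on the case report form. If the table mark means something else, such as dispensing an inhaler, label it so.
- Make the FEV1 reference for the induction steps, and the Section 9 statement, true for Visit 1 as finally described.
- In 6.1 to 6.3, state what Visit 5 minus Visit 1 and Visit 3 minus Visit 1 each estimate under that description.

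The cost is a wording amendment and at most one recorded time. The reconciliation itself needs no added subjects and no change to the test.

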10. DATA COLLECTION AND MANAGEMENT

- **Monitoring Plan:** We will use RedCap for data management. The data will be entered by one person (typically the coordinator or, for lab analysis, a lab staff member) and then checked by a second person. The data is not marked "complete" until the 2nd person verifies the entry. REDCap creates a data dictionary when the database is established, this is used as the codebook.
- **Database documentation:** All databases using equipment generated have a date and user attached to the electronic file. Data will be linked with a codebook (i.e. sample ID) using Excel. A second entry is done manually in a lab notebook, which includes date, samples assayed, assay used, any issues (like missing samples/data), reference to where data is stored, and a printout of the data (all as hardcopies in a lab notebook). Adherence to the codebook is ensured by having a second individual to check the entries. The PI takes responsibility for data management computations.
- **Case report forms:** Case report forms will be developed by the study team, using templates from previous studies. These forms are maintained by study coordinators, and reviewed by investigators as needed.
- **How will confidentiality be maintained:** Subjects will be issued a subject number when they enroll into the study, and this number will only be used to label samples. All PHI will be maintained by the study coordinator or the investigators and will be kept in locked areas when not in use. The identifiers that go into REDCap will only be accessible to those who need them for their job, specifically study physicians, investigators and coordinators. Subjects sometimes undergo procedures – such as sitting in front of the gamma camera – at the same time, however other than basic introductions, nothing about one subject is disclosed to the other subject.

11. RECRUITMENT STRATEGY

Subjects will be recruited by posters and informational emails at UNC. The study will be posted on the JOIN THE CONQUEST website, designed for recruiting subjects into research studies. "Dear Doctor" letters will be sent to pulmonary and family practices doctors who may have patients who are interested in volunteer to participate in the study.

12. CONSENT PROCESS

- **Describe the procedure that will be used to obtain informed consent/HIPAA authorization and assent (if applicable):** The study will be described in detail to the subject, including why the study is being conducted, the medication being studies, the risks and benefits, and what is expected of the subject. The subject will be given adequate time to read the consent, and consent will be obtained prior to any study procedures. Consent may take place on a separate day from the baseline procedures.
- **Who will obtain consent:** Consent will be obtained by a study coordinator or a study physician.
- **Where will consent process take place:** The consent will take place at the UNC CEMALB, located in the Human Studies Facility of the US EPA on [name] in Chapel Hill.
- **How will investigator assure that subjects comprehend the nature of the study, procedures, the risks and benefits:** The subject will be encouraged to ask questions

regarding the study and procedures. Open ended questions will be asked of the subject to solicit correct responses, to help ensure that the subject understands the study commitment, procedures and risks and benefits

13. References

14. APPENDIX

Study Personnel:

Role in Project	Name and Address	Title
Principal Investigator	[name], MS CEMALB, [name]	Professor of Pediatrics & Director, Center for Environmental Medicine, Asthma and Lung Biology
Co-investigator	[name] [name]	James C. Moeser Eminent Professor of Medicine & Director of the Marsico Lung Institute
Co-investigator	[name] CEMALB, [name]	Professor of Medicine, Director of Mucociliary Clearance and Aerosol Research Lab, CEMALB

Summary of Study Procedures:

Study Procedures	Visit 1: Baseline MCC Visit	Visit 2: (24h f/u)	Visit 3: Albuterol and MCC	Visit 4: (24h f/u)	Visit 5: Acute 7% HS	Visit 6 (24h f/u)	Study Completion visit
Time between visits	1-6 weeks		1-6 weeks		5-10 days		
Informed Consent	X						
History, med review	X		X		X		X
Review history, AEs	X	X	X	X	X	X	X
Vital Signs	X	X	X	X	X	X	X
Symptom Questionnaire	X	X	X	X	X	X	X
Physical exam	X		X		X		
Urine pregnancy test	X		X		X		
Spirometry	X	X	X	X	X	X	X
Albuterol	X		X		X		
Nebulized HS					X		
MCC Measurement	X		X		X		
24h Lung Retention Images		X		X		X	
Induced Sputum Collection	X		X		X
